
This document is confidential. Do not disclose or use except as authorized.

Determination of the Regions of Interest (ROI) in the Lumbar Spine. A. Shows the level of the axial cut through which the scan was taken. B. The elliptical area drawn around an area of the lumbar vertebral body is an ROI used to calculate the trabecular bone density.

2.4.3 *Bone Histomorphometry*

[figure not shown]
Histomorphometry is broadly defined as the measurement of the shape or form of a tissue. Bone histomorphometry is a quantitative analysis of bone structure and bone remodeling. It provides valuable information on the amount of bone and its cellular activity. *Static histomorphometry* allows quantitative evaluation of bone structure and cellular content at any particular time point. Undecalcified bone samples embedded in plastic resin are used for this purpose. Cellular content of is evaluated by immunohistochemical staining methods. Changes in bone structure and the volume of mineralized tissue are assessed by micro-computed tomography, quantitative back scatter electron imaging, and nanoindentation.

Dynamic histomorphometry provides a quantitative assessment of the extent of bone formation over a specific period of time (usually 10-14 days). If a fluorescent label, such as tetracycline, is present, it becomes incorporated into the newly formed bone, leaving a clear linear record of the site where mineralization was occurring (see Figure 7). If a second label is given 10-14 days after the first one, one can calculate the *mineral apposition rate* (MAR, mm/day) as the distance between the midpoints of the two consecutive labels, divided by the time interval between the labeling periods. The *bone formation rate* (BFR/BS, mm³/mm²/day) is the amount of newly formed bone seen under the fluorescent microscope divided by the time interval during which the label was given. We will use a quadruple labeling schedule, using two sets of double tetracycline labels which differ in color under fluorescent light. This way we will be able to distinguish the first and second label set. This technique has the great advantage that the patient can serve as his or her own pretreatment control, eliminating problems caused by the large intersite variability in histomorphometric variables [39].

CONFIDENTIAL

This document is confidential. Do not disclose or use except as authorized.

Figure 7: Visualization of Tetracycline Labeled Bone by Fluorescent Microscopy

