8. CORRELATIVE/SPECIAL STUDIES

8.1 **Pharmacokinetic Studies**

N/A

8.2 **Pharmacodynamic Studies**

N/A

8.3 **Special Studies**

8.3.1 *Blood Draws*

We will follow the trends in serological markers over a 6 month period beginning prior to the first dose or radiation received by the patient. The study Schema outlines specific time points when we plan to draw

CONFIDENTIAL

This document is confidential. Do not disclose or use except as authorized.

the blood samples. After all studies have been performed we will label the samples with a code. The key to the code will connect the sample with the subjects health information. The key to the code will be kept in a password protected computer of the principal investigator. Samples will be stored at the BioBank and Research Laboratory Services for the Maine Medical Center Research Institute.

Figure 10

What is measured:

- N-Telopeptide (NTX)
- Serum tartrate-resistant acid phosphatase 5b (TRAP5b)
- Osteocalcin (OC)
- Type 1 procollagen N-terminal (P1NP).
- PTH
- Calcium as part of a standard metabolic panel
- Phosphate

8.3.2 *Quantitative CT Scans*

Patients in both arms of the study will undergo two QCT scans. First QCT will be done at Day 1, prior to initiation of radiation treatment. Patients in the Non-Surgical Arm will undergo a second QCT at six months after their first radiation treatment. In contrast, patients in the Surgical Arm will undergo their second QCT immediately prior to surgery, 10 weeks after the first scan. Once the spinal instrumentation is introduced during the surgery, it renders the analysis impossible due to artifact. Scans will be performed by the MGH Musculoskeletal Imaging Research Core (MIRC) under the direction of [name] (Radiology). We will use the QCT Pro protocol, detailed in Section 6.1.3 – Radiation Exposure Risks. Volumetric QCT of L1, L2 and S1 vertebrae will be obtained. Images will be saved in standard DICOM format and transferred to a PACS workstation for analysis.

What is measured:

- Trabecular bone mineral density (Tb. BMD)

8.3.3 *Bone Biopsies*

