Bone biopsies will be performed on patients enrolled in the Surgical Arm of the study. Each patient will undergo two biopsies. At the time of each biopsy we plan to collect two bone samples. Figure 10 shows the location of the planned biopsy sites. The first biopsy (the control) will be taken from the iliac wing of the pelvis. This area lies outside of the radiated field, and will serve as a normal bone control. The second biopsy will be taken from the irradiated part of the sacrum. Bone biopsies will be evaluated for the end points of dynamic histomorphometry, and possible radiation-induced woven bone and bone mineralization abnormalities. Micro-CT will be performed on half of the bone samples prior to embedding to evaluate 3D trabecular microstructure. Biopsies that will be used for dynamic histomorphometry will be stored in 10% buffered formalin at room temperature in a dark space. We will send the biopsies to [name] at Columbia University for analysis. Transfers will be done in batches using FedEx. After all studies have been performed we will label the biopsies with a code. The key to the code will connect the biopsy with the subjects health information. The key to the code will be kept in a password protected computer of the principal investigator. Biopsies will be stored either at room

[figure not shown]
CONFIDENTIAL

This document is confidential. Do not disclose or use except as authorized.

temperature (embedded specimen) or frozen (fresh specimen) at the Endocrine Unit Research Laboratory of the Massachusetts General Hospital.

Figure 10 shows the location of two biopsy sites.

Figure 10: Location of the Planned Bone Biopsy Sites.

Biopsies will be done at the time of the scheduled tumor surgery. Sacral tumors are removed in stages. The first stage is done via anterior exposure, allowing access to the iliac crest. We will collect these samples first. Using a 7,5mm Rochester trephine two bone samples will be removed from the superior apex of the iliac wing in the midline (as defined as a point midway between the anterior superior and posterior superior iliac crests). In most cases, the biopsy site will be accessible through the incision made for the anterior approach. However, in those rare cases when the biopsy site is not accessible via the incision made as part of the standard of care, then a separate small incision (at most 3 cm long) will have to be made.

[figure not shown]

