The second stage is done via posterior approach, providing access to the sacrum. We will collect the second biopsy samples during the second stage procedure. Using the same 7,5mm Rochester trephine, two bone samples will be removed from bone within one centimeter of the resection margin. To avoid unnecessary damage to healthy bone, we will attempt to collect the bone samples from the part of sacrum removed in surgery. After the tumor has been resected, it is normally brought to surgical pathology by the surgeon. There the specimen is examined by the pathologist. If there is enough normal bone remaining on the resected specimen, and the pathologist feels that using the normal bone will not interfere with his

CONFIDENTIAL

This document is confidential. Do not disclose or use except as authorized.

ability to assess the margin of resection, then the biopsy will be obtained from the surgical specimen rather than from bone remaining on the sacrum still attached to the patient's spine. Figure 11 illustrates the two possible sites of the sacral biopsy.

Figure 11: Location of Sacral Biopsy Site

Sacral Biopsy. This sagittal MRI image of the sacrum shows a large tumor at the caudal end. The entire sacrum was irradiated in this patient; the extent of the radiation field is approximated by the orange outline. During surgery, an axial cut through the middle of the sacrum was made to remove the tumor with negative margins. The portion of the sacrum removed is outlined in purple. For the purposes of our study, we would always try to take the bone samples from the portion of the sacrum to be discarded (A). In those cases when the fragment removed doesn't have enough healthy tissue for a biopsy, the samples will be collected from the portion of the sacrum that remains attached to the patient's spine (B). The approximate location of the biopsy site is marked with a trephine in A and B.

8.3.4 *Undecalcified Histology*

One control and one experimental sample from the biopsies will be embedded in plastic resin (MMA/dibutylphthalate) then split in half using a fine handsaw (0.3mm kerf). So as to not alter the mechanical properties of bone, one half will be scanned by micro-CT then processed for thin section histology. The other half will be sectioned at 1 mm intervals for quantitative back scatter electron imaging followed by nano indentation.

8.3.5 *Immunohistochemistry*

CONFIDENTIAL

This document is confidential. Do not disclose or use except as authorized.

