Cellular content of bone can be evaluated by immunohistochemical staining methods. Osteoblasts will be counted on toluidine blue stained slides as blue/grey cuboidal cells in clusters at the bone surface. Osteoclasts will be counted on slides assayed for TRAP activity as TRAP-positive multinucleated cells.

What is measured:

- Osteoblast number (N.Ob/BPm, mm^{-1})
- Osteoblast surface (Ob. S/BS, %)
- Osteoclast number (N.Oc/BPm, mm^{-1})
- Osteoclast surface (Oc.S/BS, %)

8.3.6 *Micro-CT*

Undecalcified biopsies will be scanned with a micro-CT system (X-Tek HMXST 225 microfocus X-ray system, Nikon Metrology, Tring, UK).

What is measured:

- Bone volume fraction (BV/TV)
- Trabecular thickness (Tb.Th.)
- Trabecular separation (Tb.Sp.)
- Trabecular number (Tb.N.)
- Connectivity density (Conn.D)
- Structure model index (SMI)
- Trabecular bone pattern factor (TBPf)

8.3.7 *Nanoindentation*

Experimental design, data collection and analysis for nanoindentation will be done by our collaborator [name], who has the expert knowledge and experience with this technology. Bone samples for nanoindentation cannot be embedded in paraffin because it would alter the elastic properties. The portion of the biopsy specimen for nanoindentation will be collected and stored in a small amount of normal saline solution at 4°C. Bone can remain stored in this fashion for several weeks without compromising the quality of the data. Measurements will be done with a nanoindentation tester (Agilent G200 Nanoindenter, Santa Clara, CA) equipped with a diamond tip of Berkovich. The indentation will be performed with a load of 5 mN.

What is measured:

- Elastic modulus

8.3.8 *Tetracycline Quadruple Labeling*

We will use a quadruple labeling schedule, using two sets of double tetracycline labels which differ in color under fluorescent light (ie tetracycline and demeclocycline). Figure 12 shows the schedule for the administration of the bone labeling drug. This way we will be able to distinguish the first and second label

[figure not shown]
CONFIDENTIAL
This document is confidential. Do not disclose or use except as authorized.

set. This technique has the great advantage that the patient can serve as his or her own pretreatment control, eliminating problems caused by the large intersite variability in histomorphometric variables

What is measured:

- Mineral apposition rate
- Mineral formation rate
- Mineralization lag time

Figure 12: Tetracycline Administration Schedule

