The Kolmogorov–Smirnov test on the normality of the distribution of bone mineral density and trabecular bone mineral density values will be carried out in each group. To evaluate the effects of radiation, we will

CONFIDENTIAL

This document is confidential. Do not disclose or use except as authorized.

use the Student t-test and Mann–Whitney test to compare the results from the iliac crest and the sacrum. We will use the Cox stratified model to identify confounding factors.

We plan to enroll 1-2 subjects per month. Subject enrollment is limited by patient availability.

The estimated study accrual by gender, race and ethnicity is shown in the table below.

Accrual Targets				
Ethnic Category	Sex/Gender			
	Females		Males	Total
Hispanic or Latino	1	+	0	= 1
Not Hispanic or Latino	14	+	15	= 29
Ethnic Category: Total of all subjects	15	+	15	= 30
Racial Category				
American Indian or Alaskan Native	0	+	0	= 0
Asian	0	+	0	= 0
Black or African American	1	+	1	= 2
Native Hawaiian or other Pacific Islander	0	+	0	= 0
White	14	+	14	= 28
Racial Category: Total of all subjects	15	+	15	= 30

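### Biopsy measures: the iliac-versus-sacrum comparison cannot separate radiation from skeletal site, and Section 14 names no test of the before/after label data that could

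*Combined protocol and SAP*

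**What the plan says.** Section 14.2 evaluates radiation effects with a Student t-test and a Mann–Whitney test "to compare the results from the iliac crest and the sacrum". It then adds: "We will use the Cox stratified model to identify confounding factors".

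Iliac results can come only from biopsy, because for imaging Section 8.3.2 states: "Volumetric QCT of L1, L2 and S1 vertebrae will be obtained". Section 8.3.3 limits biopsies to the surgical arm and takes them at tumour surgery, the iliac samples at stage 1 and the sacral samples at stage 2. Of the iliac site it says: "This area lies outside of the radiated field, and will serve as a normal bone control". Of the other: "The second biopsy will be taken from the irradiated part of the sacrum".

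The labelling scheme is built differently. Under Section 5.2, demeclocycline is taken before radiotherapy starts and tetracycline before surgery. Section 8.3.8 says that in this way "the patient can serve as his or her own pretreatment control", and Section 2.4.3 gives the benefit as "eliminating problems caused by the large intersite variability in histomorphometric variables".

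Section 14.1.2 classes the biopsy measures as exploratory, although Sections 1.3.2 to 1.3.4 list the same questions as secondary objectives. Section 14.4 names paired tests only for PROMIS T scores. Its one other provision for exploratory variables is rank correlation with bone density. Section 2.4.5 says that sacral elastic modulus is to be measured both before and after radiation.

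**The concern.** No iliac sample is irradiated and no sacral sample is unirradiated. A difference between the two sites could be anatomical, radiation-induced or both, yet Section 14.2 presents the test as an evaluation of radiation. Read that way, an ordinary anatomical difference could be reported as a radiation effect, or could mask one.

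No decision rule rests on these endpoints. Section 14.2 does say, however, that the pilot is partly meant to supply numbers for later studies, so a mislabelled effect would be carried forward. Meanwhile surgical-arm patients take two sets of labelling drugs to create a before/after contrast for which the statistical section names no test.

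**Working it through.** **1. The plan's own figures.** Section 14.2 gives power 0.942, 0.807 and 0.469 at n = 30, 20 and 10. A two-sided paired t-test with change 10 and SD 15 (reading the printed mg/dL as mg/mL) gives 0.9416, 0.8073 and 0.4692, so they reproduce. They concern the QCT change. No power or sample size is given for the biopsy comparison.

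**2. Can radiation be separated from site?** Code site (ilium 0, sacrum 1) and radiation (no 0, yes 1).

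- One value per biopsy: the cells are ilium/unirradiated (0, 0) and sacrum/irradiated (1, 1). Intercept + site + radiation has rank 2 for 3 parameters, so radiation is not estimable.
- Sacral labels alone: first set (label 0, radiation 0), second set (label 1, radiation 1). The two columns are identical, so the rank is again 2 of 3. Radiation is aliased with label drug, calendar time and label age.
- Both label sets at both sites: four cells, with radiation equal to 1 only for the sacral second set. Intercept + site + label set + radiation has rank 4 of 4. The radiation term is (sacral second − sacral first) − (iliac second − iliac first).

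**3. Reach.** Table 1 lists 4 cell measures, 7 micro-CT measures and 1 elastic modulus, or 12 with one time point per site. Of the 3 labelling measures, apposition rate and formation rate can use the four-cell contrast. Lag time can do so only if it is obtainable for each label set.

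**4. Illustration of the confounding.** The documents give no site difference, SD or correlation, so all inputs are assumed: no radiation effect, 20 pairs, two-sided 0.05, normal data, SD 1 at each site. The unpaired t-test was simulated. The paired figures use the noncentral t with effect d/√(2(1 − ρ)). Percentage of trials declaring a radiation effect:

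| Site difference d (SD) | 0.25 | 0.5 | 0.75 | 1.0 |
|---|---|---|---|---|
| Unpaired, ρ = 0 | 12 | 34 | 64 | 87 |
| Unpaired, ρ = 0.5 | 5 | 29 | 69 | 94 |
| Unpaired, ρ = 0.7 | 2 | 25 | 73 | 97 |
| Paired, ρ = 0 | 12 | 32 | 61 | 85 |
| Paired, ρ = 0.5 | 19 | 56 | 89 | 99 |
| Paired, ρ = 0.7 | 28 | 78 | 98 | >99 |

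Pairing does not cure the confounding. Separately, with no difference of any kind the unpaired test rejects in 4.9, 2.1, 0.7 and 0.1% of trials at ρ = 0, 0.3, 0.5 and 0.7, so it discards the information in the pairing.

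**5. Precision of the difference in differences.** Assuming equal SD of change at both sites and correlation r between the changes, its SD is √(2(1 − r)) times that of the sacral change: 1.41, 1.22 and 1.00 at r = 0, 0.25 and 0.5. The 95% CI half-width for the sacral change, in SDs of change, is t(0.975, n − 1)/√n: 2.093/√20 = 0.47 at n = 20 and 2.145/√15 = 0.55 at n = 15. For the difference in differences this becomes 0.66/0.57/0.47 at n = 20 and 0.78/0.68/0.55 at n = 15.

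**6. Label age.** Section 8.3.2 implies about 70 days from first scan to surgery. First-set labels, taken 18 to 1 days before radiotherapy, are then about 70 + 1 = 71 to 70 + 18 = 88 days old at stage 1; second-set labels are 7 to 24 days old. The 70 days is approximate: the calendar's scan 3 to 5 days before surgery gives 73 to 75, and 5.5 weeks of radiotherapy plus 4 to 5 weeks of recovery gives about 67 to 74. Sacral labels are older still, by the interval between stages, which the plan does not state.

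**The case against.** - **The ilium is a deliberate control.** True, and it controls for patient and for events common to the whole skeleton. It does not control for site.
- **The undefined word for results may mean changes.** Both biopsies carry both label sets, so for the labelling outcomes Section 14.2 could mean changes compared by site, which is the difference in differences. This stands in part: for those outcomes the plan is silent rather than plainly wrong. For the 12 single-time measures no such reading exists.
- **The tests may be paired.** That they are unpaired is an inference from the unqualified Student t-test and Mann–Whitney test in 14.2, set against explicitly paired tests in 14.4. The aliasing holds either way.
- **The Cox model.** Section 14.2 does not tie it to the biopsies, so its presence says little about them. It could not separate two identical factors.

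Four stronger readings are tempting but not supported:

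- A reader might infer that the protocol itself recognised the ilium–sacrum confounding. Section 2.4.3 speaks of intersite variability but cites a study of two contiguous transiliac biopsies, which points to sampling variation rather than a systematic difference between bones.
- A reader might take the sacral before/after change as sufficient. It is aliased with drug, time and label age.
- A reader might add tumour damage as an established third confounder. Section 14.2 allows that tumours compromise bone, but under Section 8.3.3 "two bone samples will be removed from bone within one centimeter of the resection margin", and samples come from the resected specimen only if enough normal bone remains.
- A reader might extend the point to the primary endpoint. That uses two QCT scans per patient and no iliac data.

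**Conclusion.** The point holds for the exploratory biopsy measures and should be corrected before analysis. For every measure with one time point per site, radiation and site are completely aliased. This follows from the design and needs no assumed number. For apposition and formation rates the planned data would identify a radiation effect, but Section 14 names no test of it.

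That identification assumes that drug, time and label-age effects are the same at both sites on the scale analysed, and that early labels are not lost unequally by site. The stage 1/stage 2 difference weakens the assumption somewhat. The rejection rates in the table only illustrate assumed site differences and are not evidence about this trial. The loss of precision ranges from none to a factor of 1.41 over correlations from 0.5 to 0, given equal SDs of change.

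**What to change.** In Section 14:

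1. For mineral apposition rate and mineral formation rate, make the main contrast the within-patient difference in differences, (sacral second label set − first) − (iliac second − first), by one-sample (paired) t-test or Wilcoxon signed-rank test. Report the sacral change alone as supportive only, with the reason.
2. Report by site how many specimens lack a readable first or second label set. Note that the sacral biopsy is at stage 2, so its labels are older than the iliac ones by the interval between stages.
3. For static histology, micro-CT and nanoindentation, use paired iliac–sacral tests and report the result as irradiated sacrum versus unirradiated ilium, with site and radiation not separable. Treat mineralization lag time the same way if it cannot be obtained for each label set.
4. Reconcile the before-and-after wording on elastic modulus in Section 2.4.5 with Section 8.3.3, which has no pre-radiation sacral sample.

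This needs no extra biopsy, scan or drug. The costs are narrower claims for the static and mechanical measures, the loss of precision shown above, and remaining exposure to unequal label loss.

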14.1.1 Primary Endpoint

- *Outcome of interest:* change in trabecular bone mineral density (Tb. BMD) measured by QCT of the lumbar spine at the start and at the end of radiation treatment

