14.1.2 Exploratory Endpoints

- Longitudinal measurement of serum markers of bone turnover rate over 6 months
- Measurement of static and dynamic bone parameters summarized in Table 1.

Table 1: Exploratory Endpoints of the Study

Technique	Measurement
Immunohistochemistry:	Osteoblast number and surface Osteoclast number and surface

CONFIDENTIAL

This document is confidential. Do not disclose or use except as authorized.

Micro-CT :	Bone volume fraction Trabecular number Trabecular thickness and separation Connectivity density Structure model index Trabecular bone pattern factor
Nanoindentation :	Elastic modulus
Tetracycline quadruple labeling :	Mineralization lag time Mineral apposition rate Mineral formation rate

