14.2 Sample Size/Accrual Rate

Berthold and Haras published a range of normal reference values for the trabecular bone mineral density measured by quantitative CT of the lumbar spine in young adults. In healthy males and females the mean trabecular bone mineral density was 150mg /mL with a standard deviation of 20mg/mL at the start of puberty. In contrast, we expect our patients to be considerably older, to have one or many systemic illnesses, and to have tumors in the sacrum that can compromise bone quality. We expect that mean bone density at the start of the treatment in our population will be considerably lower. Assuming that it's at least 1 standard deviation less that of a normal young adult, we get an estimate of 130mg/dL at the start of treatment in all study patients. It is likely that our population will exhibit significant differences by sex owing to bone density being more affected by age in females than in males. In absence of prior studies, it is very difficult to estimate this difference. In fact, the purpose of this pilot study is in part to provide some numerical data to help guide future studies. At present, we must carry our sample size calculations keeping in mind these potential pitfalls.

The “event of interest” in this study is a change in trabecular bone density. Our hypothesis is that radiation induces loss of trabecular bone density in surgical and non-surgical patients. We would like to be able to detect a change in the average bone density of 10 mg/mL (approximately 5%) before and after radiation treatment. Assuming the standard deviation of the change we hope to observe is 15mg/dL, we get the following estimates.

Size = 30, Power = 0.942, alpha = 0.05
 Size = 20, Power = 0.807, alpha = 0.05
 Size = 10, Power = 0.469, alpha = 0.05

The main treatment arm in our patient population is the surgical patients. We plan to enroll 20 surgical patients given the results of the power analysis. The purpose of the non-surgical arm is to serve as a control for any confounding effects due to surgery. We plan to enroll 10 non-surgical patients. Smaller sample size significantly reduces the power of our analysis in the non-surgical arm. However, given that the vast majority of our patients receive surgery, the time it would take to enroll 20 patients into the non-surgical arm would undermine the purpose of doing an exploratory study to begin with.

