14.3 Stratification Factors

Patients will be stratified by the type of treatment they are undergoing (surgical vs. non-surgical).

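### The plan's only multivariable method, a stratified Cox model, fits none of the endpoints in Section 14.1, and nothing elsewhere in the plan supplies the missing event, time axis or covariates

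*Combined protocol and SAP*

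**What the plan says.** The analysis paragraph of Section 14.2 states: "We will use the Cox stratified model to identify confounding factors". That is the whole specification. The other methods in Sections 14.2 and 14.4 are a normality test, one- and two-sample tests and rank correlations, so this is the only multivariable method in the plan.

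Section 14.1.1 makes the primary endpoint the "change in trabecular bone mineral density (Tb. BMD) measured by QCT of the lumbar spine", taken at two times. Section 14.1.2 adds "Longitudinal measurement of serum markers of bone turnover rate over 6 months" and the tissue measurements in Table 1.

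Three other places bear on the model:

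- Section 14.2 labels a change in trabecular bone density the event of interest. It also mentions age, sex and systemic illness as influences on bone density.
- Section 14.3 stratifies patients by surgical or non-surgical treatment, without mentioning the Cox model.
- Section 14.2 says of the smaller arm: "The purpose of the non-surgical arm is to serve as a control for any confounding effects due to surgery".

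On scan timing, Section 8.3.2 says that "patients in the Surgical Arm will undergo their second QCT immediately prior to surgery, 10 weeks after the first scan", because instrumentation makes later scans unreadable.

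**The concern.** A Cox model relates covariates to the hazard of an event over time. Without an event, a time origin and a censoring rule it has no outcome, and Section 14.1 offers none. An analyst following the plan would have to invent the outcome, the time scale and the covariates, or drop the step.

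The pilot is meant in part to "provide some numerical data to help guide future studies". Coefficients in mg/mL for age and sex would serve that aim; a hazard ratio for an undefined event would not.

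A design limit lies behind the sentence. Surgery is the one factor that the plan calls confounding, and the non-surgical arm is there to control for it. The timing of the scans means that the primary measurement cannot contain a surgery effect.

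**Working it through.** **1. Endpoints against what a Cox model needs**

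| Endpoint (Section 14.1) | Type | Censored time to event? |
|---|---|---|
| Change in Tb. BMD, two scans per patient | Continuous, paired | No |
| Serum markers over 6 months | Continuous, repeated | No |
| Osteoblast and osteoclast number and surface | Count or percentage | No |
| Micro-CT parameters, elastic modulus | Continuous | No |
| Apposition and formation rates, mineralization lag time | Continuous biopsy values | No |

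Mineralization lag time has units of time, but it is calculated from tissue and is not a follow-up time to an event.

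**2. What the study was sized on**

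Inputs from Section 14.2: mean change 10 mg/mL, alpha 0.05, and "Assuming the standard deviation of the change we hope to observe is 15mg/dL" (read as mg/mL). A two-sided paired t-test has noncentrality (10/15)√n on n − 1 degrees of freedom:

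- n = 30: 0.942
- n = 20: 0.807
- n = 10: 0.469

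All three match the plan. One-sided t gives 0.973, 0.890 and 0.619, and two-sided normal gives 0.955, 0.847 and 0.559, so neither reproduces the set. The study was therefore sized on a paired continuous change. The plan states no number of events, hazard ratio or power for the Cox model.

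**3. Why no model recovers a surgery effect from Tb. BMD**

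Both surgical-arm scans come before surgery (Section 8.3.2). At the second scan these patients have had 50.4 Gy, at about 10 weeks. Non-surgical patients receive 72 to 77.4 Gy (Section 5). Their second scan comes six months after the first treatment by Section 8.3.2. By the calendar in Section 9.1.1 it comes about 3 months after a 7-week course: 7 + 13 = 20 weeks, about 4.6 months. An arm difference thus mixes dose, timing and patient selection. It would also be imprecise: t(0.975, 28) × 15 × √(1/20 + 1/10) = 2.048 × 15 × 0.387 = ±11.9 mg/mL, wider than the 10 mg/mL target change.

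**4. Cost of a linear model at n = 20**

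Three covariates (age, sex, baseline) leave 16 degrees of freedom in place of 19. With the residual SD held at 15:

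- Power for the mean change, covariates centred: 0.807 becomes 0.799.
- 95% CI half-width: 2.093 × 15/√20 = 7.02 becomes 2.120 × 15/√20 = 7.11 mg/mL.
- Sex coefficient at 10 v 10, sex uncorrelated with age and baseline: 2.120 × 15 × √(1/10 + 1/10) = ±14.2 mg/mL (14.9 at 7 v 13; 16.4 at 5 v 15).
- Sex coefficient at 10 v 10, assumed multiple correlation of 0.5 with age and baseline: 14.2/√(1 − 0.25) = ±16.4 mg/mL. Power for a 20 mg/mL sex difference falls from 0.80 to 0.68.

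**5. If fracture was the intended outcome**

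Section 5.7 follows patients for fracture for 12 months. Section 2.1 quotes a rate of up to 64% without a time horizon. If it applied within follow-up, 0.64 × 20 = 12.8 events. For a covariate split 10 v 10, the 95% CI for the hazard ratio is roughly the estimate divided and multiplied by exp(1.96 × 2/√12.8) = 3.0. At an assumed 20% there are 4 events and the factor is 7.1, by a large-sample formula that is unreliable at so few events. Either figure allows one or two covariates at most.

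**The case against.** The sponsor can fairly say that the plan is not empty. It names an event of interest and a stratification factor, and it lists influences on bone density: age, sex and systemic illness in Section 14.2, and PTH and 25-hydroxycalciferol in Section 2.4.1. A reader who infers that no event, strata or candidate factors appear anywhere therefore goes too far. What stands is narrower: the event is a continuous change without threshold or time axis, and neither the factor nor the influences are linked to the model.

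Three other strong readings are not supported:

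- *That the outcome and covariates will be chosen after the data are seen.* The plan is silent on when, and they could still be fixed beforehand.
- *That stratifying by arm is itself a fault because it yields no arm estimate.* The stated purpose is to identify confounders, and stratifying by arm would be ordinary adjustment.
- *That a Cox model could never be fitted to these data.* It could be applied to the ranks of the change, but the plan does not propose that and the result would not be in mg/mL.

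It can also be said that this is one exploratory sentence in a 30-patient pilot, and that deleting it would do. Deletion would remove the mismatch. It would also leave the pilot with no adjusted description of factors that the plan itself expects to matter.

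**Conclusion.** The concern holds. The plan commits its only multivariable step to a method that fits none of its listed endpoints. This is a wrong choice of method as well as missing detail, and it should be fixed. The count of time-to-event endpoints in Section 14.1 is zero.

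The harm is low to moderate. A reader might infer that the sample size or the primary result is unsound; it is not, since neither depends on this sentence and the stated power reproduces exactly.

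Separately, the change in Tb. BMD cannot reveal an effect of surgery under any model. That conclusion needs only the scan schedule. The precision figures assume an SD of 15 mg/mL, and the sex split, the correlation of 0.5 and the 20% fracture rate are illustrative assumptions.

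**What to change.** Replace the Cox sentence in Section 14.2 with text such as:

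> Factors associated with change in Tb. BMD in the surgical arm will be examined by linear regression of change on age and sex, adjusted for baseline Tb. BMD (all centred). Results will be reported with 95% CIs as descriptive, in support of the within-patient test of mean change. The baseline coefficient will not be interpreted, because of regression to the mean. The non-surgical arm will be described separately.

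Add three things:

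1. State that the within-patient test is the paired t-test implied by the power figures. The plan now names a paired t-test only for PROMIS scores (Section 14.4).
2. State that the effect of surgery on Tb. BMD cannot be estimated from these scans, and that arm differences cannot be separated from dose and scan timing.
3. If Cox was meant for fracture under Section 5.7, list time to fracture as an exploratory endpoint with its time origin, strata and handling of death, and limit the model to one or two covariates.

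The regression needs one named measurement site, so Section 1.2.1 (sacrum) and Section 14.1.1 (lumbar spine) must be reconciled first.

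The cost is a few sentences and no new measurement: baseline Tb. BMD is already taken, and age and sex are assumed to be recorded routinely. The mean change loses almost no precision. The individual coefficients will be wide, as the working shows, and should be reported as descriptive only.
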